4 STUDY DESIGN

4.1 SITES

[Medical College of Wisconsin, Milwaukee, WI](#)

4.2 INCLUSION/EXCLUSION CRITERIA

4.2.1 *INCLUSION CRITERIA*

1. Subjects will be informed about the study, have read, understood, and signed the Informed Consent Form
2. Subjects of either gender that are ≥ 18 years of age
3. Subjects who can ambulate preoperatively
4. Subjects will have a Body-Mass Index (BMI) of $\leq 40\text{mg}/\text{m}^2$
5. Subjects with an ASA classification of 1, 2 or 3
6. Subjects not receiving an epidural to control perioperative pain
7. Subjects will be undergoing elective single-staged open ventral (incisional or midline) hernia repair
8. Subjects in which intra-operatively their surgical field/wound is characterized as Type 1 (Appendix II)
9. Subjects with a hernia defect $\geq 9\text{ cm}^2$ large

4.2.2 EXCLUSION CRITERIA

1. Subjects who are not able to comprehend or comply with study requirements
2. Subjects who are pregnant
3. Subjects with BMI > 40
4. Subjects with autoimmune disorder requiring >10mg of a corticosteroid per day
5. Subjects with pre-existing systemic infections
6. Subjects with a wound-healing disorder
7. Subjects who have taken therapeutic doses of opioids for more than 7 consecutive days immediately prior to taking Alvimopan
8. Subjects who are immunocompromised such as HIV or transplant, or receiving chemo or radiation therapy
9. Subjects with a hernia defect < 9cm² large when measured intra-operatively
10. Subjects in which intra-operatively their surgical wound field/wound is characterized as Type 2, 3, or 4 (Appendix II)
11. Subjects in which the ventral incisional hernia repair requires more than one operation to reduce the hernia or to complete the hernia repair
12. Subjects with a hernia repair requiring an emergent procedure
13. Subjects in which untreated cancer was found intra-operatively
14. Subjects with cirrhosis or are currently being treated with dialysis
15. Subjects with severe hepatic impairment (Childs-Pugh class C)
16. Subjects with end-stage renal disease
17. Subjects scheduled for a concomitant procedure that involves the GI tract
18. Subjects with unplanned procedures that involve the GI tract
19. Subjects requiring post-operative NGT
20. Subjects participating in another prospective interventional study that involves the use of a device, drug, or surgery that would compromise the current study
21. Subjects with an epidural to control perioperative pain

4.3 SAMPLE SIZE

4.3.1 NUMBER OF CHARTS TO BE REVIEWED

Not Applicable.

4.3.2 NUMBER OF SUBJECTS TO BE ENROLLED

140: 70 Alvimopan, 70 Placebo

4.3.3 SAMPLE SIZE DETERMINATION

A total of 140 patients are expected to undergo research related treatments. The study will contain one open surgery arm. The open surgery arm will be a single-site prospective, randomized, double-blinded, placebo-controlled clinical trial with 1:1

randomization between the study drug and placebo with 70 patients in each group for a total of 140 patients in the study. An interim evaluation of efficacy will be conducted separately in the open surgery arm when half the patients have been recruited.

This study is expected to enroll up to 140 subjects from one academic medical center (Froedtert Hospital and the Medical College of Wisconsin) a site that performs state of the art hernia repairs and is a high volume hernia practices.

The study has been designed to provide at least 80% power to detect a 24-hour decrease in the time to return of bowel function in the treatment group compared to the control group at a one-sided 2.5% significance level. This corresponds to a two-sided 5% significance level, but acknowledges the one-sided nature of the study hypothesis. Based on data from studies of the experimental treatment in other contexts, as well as internal data, we expect a standard deviation of 48 hours. Adjusting for the increase in sample size to accommodate the planned interim analysis, 64 evaluable patients per group will provide the desired power. More details of the power characteristics are shown under the Interim Analysis section. We will recruit 70 patients in each arm to accommodate a 5-10% dropout rate.

4.4 SCREENING, RANDOMIZATION, BLINDING

4.4.1 SCREENING PROCEDURE

1. All subjects undergoing open ventral (incisional or midline) hernia repair will be approached by study staff prior to surgery to participate in the study.
2. Patients who meet all inclusion/exclusion criteria will be approached for voluntary informed consent.
3. Final determination on whether a subject will be included in the study will be made during surgery. If intra-operatively it is concluded that the subject does not meet the study criteria, the subject will be excluded and the reason will be documented.
4. The study team will maintain a screening log for all patient approached for consent per institutional IRB guidelines.

4.4.2 RANDOMIZATION

Patients will be randomized after written informed consent has been obtained and eligibility has been verified. Operationally, the blinded randomization will be carried out using patient-specific study numbers. Before the initiation of the study a list linking study IDs to treatment and control group will be generated following the randomization plan, and provided to Froedtert Hospitals Investigational Drug Services (IDS). The IDS will receive study drugs from Cubist Pharmaceuticals, Inc. and package and distribute study medications to each study patient. The patient will then receive medication dispensed from the bottle with the corresponding study ID.

4.4.3 BLINDING

The study will be performed in a double-blind fashion. The investigator, study staff, subjects, and monitors, will remain blinded to the treatment assignment. Alvimopan and the placebo will be visually identical and will be similarly packaged and administered.

The identity of the study drug may only be revealed if the subject experiences a medical emergency whose management would require knowledge of the blinded treatment assignment. The master randomization code list will be maintained by the IDS. Prior to unblinding, the surgeon or other care provider must contact the study principle investigator, and every attempt must be made by the treating surgeon to discuss the intended unblinding with the principle investigator (or a designee from IDS). All cases of unblinding, including justification for unblinding, must be fully documented by the principle investigator, site investigator, and IDS designee. The principle investigator may obtain the identity of the study drug dispensed to a subject through IDS.

If the subject becomes unblinded, the subject will continue to be followed for adverse events up to 30 days, or 14 days past discharge if the patient is an inpatient after 30 days, but the efficacy data from this point will be carried forward and analyzed in the intent-to-treat analysis.

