3.2 STUDY ENDPOINTS

3.2.1 PRIMARY ENDPOINT:

[Length of time \(hrs/days\) to gastrointestinal tract recovery](#)

3.2.1.1 PRIMARY ENDPOINT DEFINITION:

Time to gastrointestinal recovery will be measured by the following: Time to first flatus, time to toleration of a liquid diet, time to toleration of a solid diet, time to toleration or oral pain medications, time to first bowel movement, time to GI-2 recovery, time to GI-3 recovery, incidence of nasogastric tube insertion, episodes of emesis, use of anti-nausea medication, nausea, bloating, incidence of diet reduction or restriction, and initiation of TPN.

Time to first flatus and time to first bowel movement are patient reported endpoints that occur during the hospitalization. Patients will be asked about flatus twice daily by the physician or a qualified study or clinical staff member. Additionally, patients will be instructed to notify the nurse following first flatus and/or bowel movement so that the time can be recorded.

Toleration of a diet and toleration of oral pain medication are defined as ingestion of diet or medications that occurs without vomiting or significant nausea for four hours following ingestion.

GI-2 recovery is defined as both toleration of solid food and occurrence of first bowel movement. GI-3 recovery is defined as toleration of solid food and either occurrence of first flatus or occurrence of first bowel movement.

Patients requiring nasogastric tube insertion, requiring reduction or restriction of diet, having episodes of emesis, and/or needing initiation of TPN will be recorded. VAS

nausea, bloating and pain scores will be recorded by nursing staff at least twice each day. The number of doses of anti-nausea medication administered during the hospitalization will also be recorded.

3.2.2 *SECONDARY ENDPOINT(S):*

[Length of hospital stay](#), 30-day treatment related morbidity and re-admission rates, and post-operative pain scores.

3.2.2.1 *SECONDARY ENDPOINT DEFINITION(S):*

Length of stay will be measured in hours from the time that surgery is completed until the hospital discharge order is written (hrs/days).

Treatment related morbidity and re-admission rates will be assessed from the time surgery is completed to 30-days post-operatively. Treatment related morbidity and re-admission rates include: POI, indigestion, and any event determined by the attending physician to be directly related to treatment.

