6.3 DATA / STATISTICAL ANALYSIS

All efficacy analyses will be intent to treat. The time to bowel function recovery and hospital length of stay will be compared between the two groups using Student's t-test. Due to the short-term nature of the outcome measures we expect no censoring.

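### The plan carries efficacy data forward after unblinding; read as a last-value rule, this does not suit elapsed-time endpoints and could understate times for patients not yet recovered or discharged

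*Combined protocol and SAP*

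**What the plan says.** Section 4.4.3 (Blinding) restricts unblinding: "The identity of the study drug may only be revealed if the subject experiences a medical emergency", and the emergency must be one whose management depends on knowing the assignment. After unblinding, "the subject will continue to be followed for adverse events up to 30 days, or 14 days past discharge" (the longer period applies to a patient still in hospital after 30 days). The sentence then turns with a *but*: "the efficacy data from this point will be carried forward and analyzed in the intent-to-treat analysis". What *carried forward* means is not explained there or elsewhere.

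Section 3.2 defines the primary endpoint mainly through elapsed times: "Time to gastrointestinal recovery will be measured by the following: Time to first flatus, time to toleration of a liquid diet", followed by solid diet, oral pain medication, first bowel movement, GI-2 and GI-3, together with several incidence and symptom items. Length of stay, a secondary endpoint, runs in hours from the end of surgery to the discharge order.

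Section 6.3 states "All efficacy analyses will be intent to treat". It continues: "The time to bowel function recovery and hospital length of stay will be compared between the two groups" by Student's t-test, and "Due to the short-term nature of the outcome measures we expect no censoring". It gives no rule for a recovery or discharge time that was not observed.

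**The concern.** Section 4.4.3 names only adverse-event follow-up as continuing, and sets efficacy data against it with *but*. Together with *carried forward*, which is the usual term for last-value imputation, this reads as an instruction to fix the efficacy outcome at unblinding.

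That can make sense for a score measured repeatedly. It does not make sense for a time to an event. Before the event there is no value to carry, only the fact that it has not yet happened. If the hours elapsed so far are entered as the outcome, a patient who has not recovered is analysed as having recovered at that moment. A t-test needs one number per patient, and Section 6.3 offers no other rule, so the sentence in Section 4.4.3 is the only text that covers these patients.

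Unblinding follows an emergency, so the affected patients would be a group selected after randomisation, possibly unequally by arm. An error confined to one arm passes directly into the difference in means.

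**Working it through.** **Inputs from the plan.** Section 4.3.3: difference 24 h, SD 48 h, one-sided 2.5%, 64 evaluable per arm, "at least 80% power to detect a 24-hour decrease in the time to return of bowel function". Section 6.1: one interim analysis at half information with a third-degree power spending function.

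**The plan's own figures first.**
- Fixed design without an interim analysis: 63 per arm.
- Alpha spent at the interim: 0.025 × 0.5³ = 0.003125.
- Standard error of the difference with 64 per arm: 48 × √(2/64) = 8.49 h. The expected final z is 24/8.49 = 2.83.
- Two-stage normal calculation with 64 per arm: 23.1% at the interim, 57.2% at the final analysis, 80.4% overall. Section 6.1 gives 22.9%, 57.1% and 80.0%. The design reproduces closely.

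**What each reading does to a patient unblinded in hospital.**

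| Status at unblinding | Last-value reading | Later data retained as randomised |
|---|---|---|
| Recovered and discharged | no effect | no effect |
| Recovered, still in hospital | recovery time unaffected; no length of stay to carry | no effect |
| Not recovered | neither a recovery time nor a length of stay to carry | no effect |

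**Size if elapsed time is entered as the outcome.** The documents give neither the number unblinded nor the hours lost, so both are assumptions. With k patients in one arm of 64, each recorded D hours too short:

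shift in that arm's mean = k × D / 64

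- Low end: 1 × 48/64 = 0.75 h; 0.75/24 = 3%.
- High end: 3 × 120/64 = 5.6 h; 5.6/24 = 23%.

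The same two-stage boundaries, with the SD held at 48 h, give the effect on the test of recovery time:

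| k | D (h) | Shift (h) | % of 24 h | Power if all in placebo arm | One-sided type I error if all in alvimopan arm |
|---|---|---|---|---|---|
| 0 | – | 0 | 0 | 80.4% | 2.5% |
| 1 | 48 | 0.75 | 3 | 77.8% | 3.1% |
| 2 | 48 | 1.5 | 6 | 75.1% | 3.7% |
| 2 | 96 | 3.0 | 12.5 | 69.2% | 5.4% |
| 3 | 96 | 4.5 | 19 | 62.8% | 7.6% |
| 3 | 120 | 5.6 | 23 | 57.6% | 9.6% |

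Power is computed at a true difference of (24 − shift), and type I error at an apparent difference equal to the shift. If numbers and errors are equal in the two arms, the difference in means does not move.

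**The case against.** The strongest reply is that the sentence can be read in a valid way. Its object is the efficacy data *from this point*, whereas a last-value rule would carry data from before it. On that reading, data collected after unblinding are taken into the intent-to-treat analysis in the assigned arm, and the bias is zero. Other sections fit this. Section 3.2 has staff asking about flatus twice daily and recording event times, and it defines length of stay with no exception for unblinding. Section 6.3 expects no censoring, which is consistent with recording until recovery. This reading cannot be excluded. It leaves the *but* and the word *carried* with little purpose, however, and nothing in the plan confirms it.

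A reader might go further and infer that the plan will record too-short times in its sickest patients. The documents do not support that:
- No section enters the unblinding time as the recovery time. The last status of an unrecovered patient is simply not recovered, which is a missing or censored time.
- That unblinded patients recover more slowly is inferred from the emergency criterion. The criterion is also narrow, because the emergency must require knowledge of the assignment.
- Recovery times already reached before unblinding are unaffected.
- The high end of the range needs three unblinded patients, all in one arm, each 120 h short, which is 2.5 times the planned SD.

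Nor does the sentence abandon intent to treat in the sense of allocation, since patients stay in their assigned arm. What is in doubt is the value analysed for them. All of these limits stand.

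**Conclusion.** The point holds in a limited form. Section 4.4.3 states a rule for efficacy data after unblinding. Under its more natural reading, that rule cannot be applied properly to time to gastrointestinal recovery or to length of stay when the event is still to come. Under its other reading it is sound but not clearly expressed, which leaves the handling open to choice after an assignment has been revealed.

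The effect may be nil: no one may be unblinded, later data may be retained, or errors may balance across arms. The range of 0.75 to 5.6 h (3% to 23% of the target difference) rests on three assumptions: 1 to 3 affected patients in a single arm of 64, times 48 to 120 h too short, and elapsed time entered as the outcome. Shortened times in the placebo arm would mask a benefit; in the alvimopan arm they would create or enlarge one. The documents do not say which is more likely. The sentence should be changed because the planned power of 80.0% leaves little margin and the correction costs almost nothing.

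**What to change.** In Section 4.4.3, delete the carry-forward clause and replace it with wording such as: *After unblinding, the actual times to gastrointestinal recovery and to discharge continue to be recorded and are analysed in the assigned arm. No value is imputed from the time of unblinding.*

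In Section 6.3, reconcile the expectation of no censoring with this: *Censoring is not expected. Any recovery or discharge time that is never observed will be treated as censored at the last observation in a time-to-event sensitivity analysis.*

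Do not add an analysis that leaves out unblinded patients. It would select on an event after randomisation and could introduce a bias of its own.

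The cost is a sentence or two in each section and one small sensitivity analysis if any time is unobserved. No extra data collection is needed, since event times are already to be recorded during the hospital stay.

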4.5 REGULATORY AND ETHICS

4.5.1 INFORMED CONSENT

Voluntary written informed consent must be obtained before any study-related procedures are performed in accordance with International Conference on Harmonization (ICH) guidelines and the requirements of informed consent (Title 21 Code of Federal Regulations (CFR) Parts 50.20 and 50.25). Consent must be documented by the use of a written consent form approved by Cubist and the Institutional Review Board (IRB) in accordance with Title 21 CFR Part 50.27. In the case of non-interventional studies, a waiver of informed consent may be granted by your IRB and will need to be provided to Cubist. A technical guide is available upon request to assist you in understanding informed consent requirements.

All patients who meet inclusion criteria and voluntarily agree to participate in the study will sign an IRB approved informed consent.

4.5.2 INSTITUTIONAL REVIEW BOARD/ETHICS COMMITTEE

The Medical College of Wisconsin IRB will oversee the proposed study.

4.5.3 INVESTIGATIONAL NEW DRUG (IND) FILING

As the Sponsor Investigator you are responsible for determining whether an IND is necessary in order to conduct your proposed clinical study. Cubist Pharmaceuticals does not make this determination for Sponsor-Investigator studies. We strongly encourage you to contact the Food and Drug Administration (FDA) for assistance in determining the necessity of an IND. Information on who to contact can be found by clicking the following link: [IND Guidance](#). Section 312.2 of Title 21 of the Code of Federal Regulations details the applicability and exceptions of the IND regulations. A technical guide is available upon request to assist you in understanding when an IND may be required.

The study team submitted an IND application to the FDA to support our study.

5 STUDY PROCEDURES

5.1 TREATMENT

Consented patients in the Treatment Group will receive 12 milligrams (mg) of Alvimopan per-oral (PO) 30 minutes to 90 minutes prior to ventral hernia repair in the pre-operative area and continue 12 mg PO twice daily until hospital discharge or post-operative day (POD) 7 for a maximum of 15 in-hospital doses (Appendix II).

Patients in the Control Group will receive 12 milligrams (mg) of Placebo orally (PO) 30 minutes to 1 hour prior to VHR in the pre-operative area and continue 12 mg PO twice a day until hospital discharge or post-operative (POD) 7 for a maximum of 15 in-hospital doses.

If the maximum allowed number of doses is not achieved in a seven day period (15 doses) the remaining study medication is to be returned to FH IDS for proper disposal. Under no circumstances is study medication to be re-used or re-packaged for sale or distribution.

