3 STUDY OBJECTIVES AND ENDPOINTS

3.1 STUDY OBJECTIVES

3.1.1 PRIMARY OBJECTIVES:

Primary Objective: To investigate the efficacy and safety of Almimopan, 12mg, administered orally 30 to 90 minutes preoperatively and twice daily postoperatively for a maximum of 7 days (15 total doses) in conjunction with a standardization postoperative care pathway for managing postoperative ileus after ventral hernia repair.

3.1.2 SECONDARY OBJECTIVES:

Secondary Objective: To investigate the post-operative gastrointestinal recovery, and treatment related morbidity after ventral hernia repair.

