5.3 PROCEDURES

Patients who meet all inclusion criteria will undergo the study related procedures stated below.

During enrollment, FH IDS will assign medication to patients in order of enrollment and according to the randomization code list. The patient will then receive medication dispensed from the bottle with the corresponding study ID.

Patient treatment will follow (section 5.1).

Following surgery, patients will be admitted to the hospital and a basic standardized treatment pathway will be initiated.

- 1) Following surgery patients are admitted with NPO status, PRN IV opioid pain medication, and PRN IV anti-nausea medication.
- 2) Epidural use is up to the discretions of the treating surgeon.
 - a. Non-narcotic adjuncts can be used as determined by the physician

- 3) Nasogastric tubes are NOT routinely left in following surgery. However, nasogastric tube use is up to the discretion of the treating surgeon. Patients who require NGT will be excluded from the study.
- 4) Patients remain NPO until the following criteria are met: reported flatus, absence of nausea and/or emesis and/or bloating, and absence of abdominal distention. Alternatively, clinical determination made by the physician can be utilized for diet advancement. If clinical determination outside of these parameters is used then the justification for the clinical decision making will be recorded for these patients.
- 5) Transition to oral pain medication will occur at or after the time of transition to clear liquids.
- 6) Diet advancement after clears will occur at physician discretion
- 7) Minimum discharge criteria include: toleration of diet beyond clears, toleration of oral pain medication, and absence of nausea/vomiting/distention.
 - a. Toleration of solid food is NOT required for discharge
 - b. Production of a bowel movement is NOT required for discharge

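### Section 5.1 gives the two arms different pre-operative dosing windows, which contradicts the blinding section; disclosure of the arm is a conditional risk

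*Combined protocol and SAP*

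**What the plan says.** All references are to the combined protocol and SAP.

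- **Section 5.1, alvimopan paragraph:** the pre-operative dose is given "30 minutes to 90 minutes prior to ventral hernia repair in the pre-operative area".
- **Section 5.1, placebo paragraph:** the pre-operative dose is given "30 minutes to 1 hour prior to VHR in the pre-operative area". The rest of the schedule (twice-daily dosing to discharge or day 7, at most 15 doses) is the same in both paragraphs.
- **Section 3.1.1:** the primary objective describes alvimopan as "administered orally 30 to 90 minutes preoperatively and twice daily postoperatively". It does not mention placebo.
- **Section 4.4.3:** "The investigator, study staff, subjects, and monitors, will remain blinded to the treatment assignment". On handling, "Alvimopan and the placebo will be visually identical and will be similarly packaged and administered". On the code, "The master randomization code list will be maintained by the IDS".
- **Section 5.3:** treatment is referred back to section 5.1, and "The patient will then receive medication dispensed from the bottle with the corresponding study ID".

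No supplied section explains the difference between the windows or says how blinded staff should treat it. Section 5.1 also cites Appendix II in its alvimopan paragraph. That appendix is not in the text available for this review, so whether it states a common schedule could not be checked.

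**The concern.** In a double-blind trial the dosing instruction should read the same for every patient. Here it depends on the arm, although the people who give the dose and those who monitor it are not supposed to know the arm. Section 5.3 makes section 5.1 the operative instruction, so the difference cannot be set aside as background text.

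Two things are at stake. The first is compliance: for some dose times, whether the protocol was followed depends on an assignment that blinded staff and monitors cannot see. The second is the blind itself, if the arm-specific windows were ever put into practice or used to log deviations.

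The blind matters for these endpoints. Under section 3.2.1.1, flatus and bowel movement are reported by patients. Under section 5.3, diet advancement beyond clear liquids is left to the physician, and the discharge criteria are only minimums. Under section 3.2.2.1, length of stay ends when the discharge order is written. Knowledge of the arm could influence any of these.

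**Working it through.** The plan states no figure on this point, so there is none to reproduce. The check compares the windows and then asks what follows under each way of running the trial.

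**Inputs.** Alvimopan window 30 to 90 minutes and placebo window 30 to 60 minutes (section 5.1); 70 patients per arm, 140 in all (section 4.3.2). The documents give no distribution of dose times, so any share of doses in a given band is an assumption.

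**Step 1: the windows.**

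- Alvimopan span: 90 − 30 = 60 minutes.
- Placebo span: 60 − 30 = 30 minutes.
- Overlap: 30 to 60 minutes, which is the whole placebo window.
- Part allowed for alvimopan only: 90 − 60 = 30 minutes, or 30/60 = 50% of the alvimopan window.

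| Time before surgery | Alvimopan | Placebo | Classifiable without the code? |
|---|---|---|---|
| 30 to 60 min | complies | complies | yes |
| over 60, up to 90 min | complies | deviates | no |
| under 30 or over 90 min | deviates | deviates | yes |

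**Step 2: dosing times alike in both arms.** Suppose staff use the same timing for everyone, within 30 to 90 minutes. Let p be the share of doses given more than 60 minutes before surgery.

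- Placebo deviations from the written text = p × 70. Alvimopan deviations = 0.
- p = 0 gives 0 × 70 = 0; p = 1 gives 1 × 70 = 70.

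The documents do not narrow the range of 0 to 70. In this scenario the dose time carries no information about the arm. The assignment could leak only if someone with the code marked the placebo doses as deviations.

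**Step 3: arm-specific windows applied.** Suppose instead that someone with the code imposed the two windows. Let q be the share of alvimopan first doses given more than 60 minutes before surgery. Each such dose would identify its patient as being on alvimopan.

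- Share of all patients identified = q × 70/140 = q/2.
- Probability of alvimopan, given a dose at 30 to 60 minutes = (1 − q) / [(1 − q) + 1], against 50% without the timing information.

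| q (assumed) | Patients identified | P(alvimopan), dose at 30–60 min |
|---|---|---|
| 0.25 | 12.5% | 0.75/1.75 = 43% |
| 0.50 | 25% | 0.50/1.50 = 33% |
| 0.75 | 37.5% | 0.25/1.25 = 20% |

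The consequences in Steps 2 and 3 belong to different ways of running the trial and should not be added together.

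**Step 4: effect on the analysis.** Section 6.3 makes all efficacy analyses intent to treat, so timing deviations remove nobody from the comparison. The sample size in section 4.3.3 rests on a 24-hour difference, a 48-hour standard deviation and a one-sided 2.5% level. None of these involves dose timing.

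**The case against.** The best defence is that this is a drafting slip with no necessary consequence. Section 4.4.3 shows that like handling was intended, and the described role of the Investigational Drug Services is to assign, package and distribute medication by study ID. No section has it issue timing orders by arm. Much of this stands, and it rules out four stronger readings that a reader might infer.

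- **That blinded staff cannot comply at all.** They can: the placebo window lies wholly inside the alvimopan window, so a dose at 30 to 60 minutes satisfies both texts in either arm. What remains is that the protocol does not state this, and staff working to the longer window would have no warning.
- **That the blind will be broken.** Disclosure needs a person with the code to apply or log the arm-specific windows. The documents describe no such step.
- **That about half the placebo arm, 0.5 × 70 = 35 patients, would be logged as deviations against none on alvimopan.** That figure assumes times spread evenly over 30 to 90 minutes in both arms. The documents give no basis for the assumption, and in that scenario dose time itself reveals nothing about the arm.
- **That a per-protocol comparison would be distorted.** No per-protocol set is defined; section 6.3 plans intent-to-treat efficacy analyses only.

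The drafting-slip explanation is plausible, but the documents do not confirm it. Section 3.1.1 cannot settle the matter because it is silent on placebo. A slip in the governing dosing instruction still has to be corrected.

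**Conclusion.** The point holds as an internal contradiction between sections 5.1 and 4.4.3, subject to what Appendix II may say. For doses given more than 60 and up to 90 minutes before surgery, compliance depends on the arm and cannot be judged without the code. This follows from the text alone and needs no assumption.

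The practical size is unknown. Under common timing the number of placebo deviations lies between 0 and 70. The shares of patients identifiable from dose time (12.5% to 37.5% for the assumed values of q) apply only if the arm-specific windows were actually put into effect. Unblinding is therefore a conditional risk. It deserves attention because the outcomes are patient-reported or discretionary, and because the correction is nearly free. The planned primary comparison, the sample size and the power do not change.

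**What to change.** Reconcile sections 3.1.1, 4.4.3 and 5.1 so that one identical window, stated for all study medication without reference to arm, applies to every patient. Which window that should be is for the sponsor to confirm; this review takes no position. Check Appendix II against the same statement. Judge timing deviations against that single window, so that blinded staff and monitors can classify every dose without the code.

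The cost is about one sentence in the protocol and a matching update to the pharmacy order set. It adds no patients or procedures and leaves the statistical analysis as planned.
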